------------------------	--

Study Objectives: Primary: Secondary:	
The study's primary efficacy endpoint will be the proportion of responders at the end of treatment, which may be up to between 24 weeks/6 months to 72 weeks/18 months of treatment, with response defined as 50% or greater hair re-growth from baseline as assessed by SALT score at the end of treatment - week 24 to 72. This is a relatively strict definition for defining responders and non-responders and was chosen to minimize the potential for spontaneous remission, in which fewer than 10% are expected to achieve this magnitude of hair regrowth spontaneously.
 
As additional secondary endpoints, efficacy will be measured by changes in hair re-growth as a continuous variable as determined by physical exam and Canfield photography, as well as patient and physician global evaluation scores. To assess the durability of responses, patients will continue to be followed for an additional 6 months after treatment is completed. Response at the end of study, week 72-96, will be examined as a secondary outcome. We will compare the efficacy of tofacitinib in promoting hair regrowth in patients with moderate to severe patch type alopecia areata to the efficacy in treating patients with current alopecia totalis (AT) or universalis (AU).

Study Design:	
Open-label pilot study of tofacitinib 5mg to 10mg PO BID, for 6 to 18 months in the treatment of moderate to severe AA, and alopecia totalis or universalis, followed by 6 months follow-up off drug to assess for delayed response to treatment and/or the incidence and timing of recurrence of disease.
 
The initial treatment dose will be tofacitinib 5mg PO BID, and may be increased up to 10mg PO BID, if clinically indicated at the discretion of the investigator.
 
The initial treatment duration will be 6 months, and may be extended by up to 12 additional months if clinically indicated with an acceptable lab safety profile, at the discretion of the investigator.

Study Schema Drugs / Doses / Length of Treatment)	
Tofacitinib (5 mg to 10 mg) will be taken orally twice a day for up to 24 to 72 weeks.
 
Study drug dose may be reduced and/or temporarily discontinued if indicated based upon laboratory values.

Accrual Goal: (Total number of subjects)	15

Accrual Rate: (Number of subjects expected per month)	1-3

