To our knowledge, tofacitinib has never been examined in human AA except for a single case report of the treatment of a patient with alopecia universalis and psoriasis with tofacitinib. That patient reportedly regrew all scalp and body hair. We propose an open-label clinical trial to test the safety and efficacy of tofacitinib 5mg to 10mg orally, twice-daily dosing for up to 6 to 12 months, in the treatment of 15 subjects diagnosed with moderate to severe patch-type AA and/or AT/AU. This initial clinical experience with tofacitinib, if positive, would provide the basis for considering and designing subsequent larger and appropriately powered RCTs.

The study proposed here targets the identical moderate-severe AA patient population as two other preceding RCT studies that also evaluated therapeutic effects of immune biologics (alefacept and efalizumab) (Price et al, 2008; Strober et al, 2009). In addition, we propose an exploratory substudy in a small group of patients with AT/AU.

Since the initial writing of this protocol new preliminary findings have noted significant hair regrowth in patients who are treated with tofacitinib at a dose of 10mg PO BID. Based on previously a published report of successful treatment of alopecia areata with tofacitinib (JID June 2014. Killing Two Birds with One Stone: Oral Tofacitinib Reverses Alopecia Universalis in a Patient with Plaque Psoriasis. [name] and [name], PhD. Department of Dermatology, Yale University School of Medicine, New Haven, CT.) and subsequent unpublished information from [name] and other investigators using tofacitinib in the treatment of alopecia areata, it is evident that a longer course of treatment may be needed, for some patients to achieve full response. In addition, there have not been serious adverse effects noted in this study, or per the unpublished reports of other investigators who have used tofacitinib for extended periods in patients with alopecia areata. Therefore it appears that increasing the duration of treatment may be beneficial in some patients and is well tolerated.

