## **5 STUDY OBJECTIVES**

### **5.1 Primary Objective**

The study’s *primary efficacy endpoint* will be the proportion of responders at the end of treatment, after up to 24 weeks/6 months to 72 weeks/18 months of treatment, defined as 50% or greater hair re-growth from baseline as assessed by SALT at week 24 to 72. This is a relatively strict definition for defining responders and non-responders and was chosen to minimize the potential for spontaneous remission, in which fewer than 10% are expected to achieve this magnitude of hair regrowth spontaneously.

The duration of treatment will be up to 6 to 18 months, at the discretion of the investigator, dependent on individual subject response as well as safety considerations.

To assess the durability of responses, patients who achieve 50% regrowth from baseline during the first 6 to 18 months, will continue to be followed for an additional 6 months off treatment or until it is determined that relapse has occurred.

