#### 8, 16, and 24 weeks after end of treatment (follow-up period off study medication)

All patients will be seen at 8, 16, and 24 weeks after completion of study drug, to determine durability of response or evidence for a delayed effect. Importantly patients who achieved  $\geq 50\%$  regrowth as measured by SALT score (responders) will be seen at 8, 16, and 24 weeks after end of study treatment in order to assess the frequency and timing of relapse or to capture the occurrence of further regrowth.

Relapse will be defined as any recurrence of hair loss in responders (subjects achieving greater than 50% decrease in SALT score from baseline during the first 6 to 18 months of the study) who had achieved stable regrowth without continued loss for at least 2 months; and loss of  $\geq 25\%$  of regrowth in patients who had achieved 50% regrowth during treatment but still had chronic low grade hair loss.

Nonresponders will also be offered the option to continue follow-up in order to assess for delayed response. Efficacy evaluations: SALT, PGA, Patient global assessment and patient quality of life assessment will be performed.

Blood draws for safety parameters will be conducted at 8 weeks after end of treatment if deemed necessary to assess normalization of any previously abnormal values.

Adverse events will be assessed at every visit.

Standardized photographs of the subject's scalp will be taken at every visit; blood draws for safety parameters and immune studies will be done based on the attached table of study procedures. Photographs will be used to support determination of percent hair regrowth. Photography will be performed using a high resolution digital camera with Intellistudio system from Canfield Scientific, Inc., Patients will be positioned using a laser guide, after which photographs of the entire scalp will be taken at standardized locations and at a fixed distance. Close-up photographs may also be taken using an epiluminescent attachment in order to assess for the presence of early regrowth.

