#### Unscheduled Visits

An unscheduled visit can occur at any time during the study for instance as prompted by signs of infection or local injection site reactions. A source document must be maintained for these unscheduled visits. The date for the visit and any data generated must be recorded on the

appropriate CRF. At treatment discontinuation/early termination subjects will undergo end of study evaluations per the Schedule of Assessments.

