## **7.7 Discontinuation of Subjects from Treatment**

Subjects MUST discontinue study treatment and withdraw from the study for any of the following reasons:

- Withdrawal of informed consent (subject's decision to withdraw for any reason)
- Any clinical adverse event (AE), laboratory abnormality, or intercurrent illness which, in the opinion of the investigator, indicates that continued participation in the study is not in the best interest of the subject
- Pregnancy
  - Instruct WOCBP to contact the investigator or study staff immediately if they suspect they might be pregnant (e.g., missed or late menstrual period) at any time during study participation. Institutional policy and local regulations should determine the frequency of on-study pregnancy tests for WOCBP enrolled in the study.
- Loss of ability to freely provide consent through imprisonment or involuntarily incarceration for treatment of either a psychiatric or physical (e.g., infectious disease) illness.

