## 11 EFFICACY ASSESSMENT

### 11.1 Primary Efficacy Assessment

The study's *primary efficacy endpoint* will be the proportion of responders after 6 months of treatment, with response defined as 50% or greater hair re-growth from baseline as assessed by SALT score (Figure 6) at week 24. This is a relatively strict definition for defining responders and non-responders and was chosen to minimize the potential for spontaneous remission, in which approximately 8% or less are expected to achieve this magnitude of hair regrowth spontaneously.

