### 13.3 Endpoint Definitions

1. The study's *primary efficacy endpoint* will be the proportion of responders after 6 to 18 months of treatment, with response defined as 50% or greater hair re-growth from baseline as assessed by SALT score at week 24 to 72.

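### The primary response rate has two time points (week 24 in 11.1, end of treatment at week 24 to 72 elsewhere), and no text says how a patient who stops before week 24 counts

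*Combined protocol and SAP*

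**What the plan says.** Four current passages define the primary endpoint.

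- Protocol Synopsis, Study Objectives: "proportion of responders at the end of treatment, which may be up to between 24 weeks/6 months to 72 weeks/18 months of treatment".
- Section 5.1: "the proportion of responders at the end of treatment, after up to 24 weeks/6 months to 72 weeks/18 months of treatment". It adds that the investigator sets the duration, depending partly on how the individual patient responds.
- Section 13.3: "with response defined as 50% or greater hair re-growth from baseline as assessed by SALT score at week 24 to 72".
- Section 11.1: response after 6 months, "as assessed by SALT score (Figure 6) at week 24".

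Secondary outcomes 1 to 3 (sections 5.2, 11.1.1 and 13.3) use the end-of-treatment window. Section 9.1 labels the week 24 visit as the end of treatment, and then lists optional treatment visits from week 28 to week 72.

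For patients who stop early, section 7.1 (Unscheduled Visits) says: "At treatment discontinuation/early termination subjects will undergo end of study evaluations per the Schedule of Assessments". The Early Termination list in 9.1 includes SALT. Section 13.2, headed as the analysis populations, contains only an accrual paragraph. Section 13.4.3 describes descriptive summaries and has no rule for missing values or early stopping. Section 13.3 asks only that the proportion who discontinued be summarized.

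**The concern.** The response rate is this trial's main product. Section 13.4.3 says that the descriptive results will help to design later trials, and secondary outcome 2 in 13.3 compares the rate with a historical rate below 10%. With 15 patients, each one is worth 1/15 = 6.7 percentage points.

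The two definitions agree for a patient who finishes at week 24. They can differ for anyone who enters the extension, and the protocol expects that to matter: section 4 says "it is evident that a longer course of treatment may be needed, for some patients to achieve full response". Following the plan as written therefore yields two primary rates, with nothing to say which is the reported one. In an open-label study, that choice could be made after the results are known.

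The same freedom exists for a patient who permanently stops drug before week 24. That patient may have a SALT value from early termination. Three treatments are open: use that value, count the patient as a non-responder, or leave the patient out. Leaving such patients out can only raise the rate, or leave it unchanged, compared with counting them as non-responders.

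**Working it through.** **Inputs.** n = 15, null rate 10%, alternative 48%, type I error 5% (section 13.1; sidedness not stated). The second scenario there is 30% against 73%. I read 48% and 73% as true rates. The documents name no test and give no dropout rate, so the exact one-sided binomial test and every count and stopping rate below are assumptions.

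**Plan's own figure.** The rule is to reject when X ≥ r, with r the smallest count for which P(X ≥ r | 15, p0) ≤ 0.05.
- p0 = 0.10: P(X ≥ 4) = 0.0556 and P(X ≥ 5) = 0.0127, so r = 5. Power = P(X ≥ 5 | 15, 0.48) = 92.0%.
- p0 = 0.30: P(X ≥ 9) = 0.0152, so r = 9. Power at 0.73 = 91.8%.

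The statement of more than 80% power holds in both cases when all 15 patients are evaluable.

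**Time point.** Suppose 4 patients respond at week 24, 2 more cross 50% during the extension, and no response is lost.

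| Definition | Rate | 95% CI (Clopper-Pearson) | p v 10% |
|---|---|---|---|
| Week 24 (11.1) | 4/15 = 26.7% | 7.8 to 55.1% | 0.056 |
| End of treatment (synopsis, 5.1, 13.3) | 6/15 = 40.0% | 16.3 to 67.7% | 0.002 |

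The difference is 2/15 = 13.3 points. With 5 or more responders at both time points, both results pass the cut-off (5/15 gives p = 0.0127) and only the estimate changes. If the true rate is 48%, the chance of exactly 4 of 15 is 0.054, so a result just below the cut-off is possible but not likely.

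**Early stopping, effect on the estimate.** Suppose 3 of 15 stop before week 24, one of them has at least 50% regrowth at early termination, and 6 of the other 12 respond.
- Stoppers as non-responders: 6/15 = 40.0%, p = 0.0022.
- Early-termination SALT used: 7/15 = 46.7%, p = 0.0003.
- Stoppers left out: 6/12 = 50.0%, p = 0.0005.

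The estimate moves by up to 10 points, and all three results reject 10%.

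**Early stopping, effect on power.** If stoppers count as non-responders and 48% of the rest respond, the effective rate is 0.48 × (1 − d), and power is P(X ≥ 5 | 15, 0.48 × (1 − d)).

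| Assumed early stopping d | Effective rate | Power |
|---|---|---|
| 0% | 0.480 | 92.0% |
| 10% | 0.432 | 84.9% |
| 15% | 0.408 | 80.1% |
| 20% | 0.384 | 74.4% |
| 30% | 0.336 | 60.4% |

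Power equals 80% at d = 15.1%.

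**The case against.** The strongest reply is that 11.1 is a leftover. Three of the four definitions, and the secondary outcomes, use end of treatment, so the intention is fairly clear. That is a good reason to choose end of treatment when reconciling. It does not remove the conflict, because 11.1 is the section on the primary efficacy assessment and is operative text.

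A second reply is that the efficacy analysis is descriptive and no test is named. This stands as a limit on size: the p-values above rest on a test that I supplied, and the comparison with 10% changes only near the cut-off. The rate itself is still what later trials would use.

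A reader might also infer that 7.7 removes every patient who stops drug from the study, so that early stoppers have no usable SALT. Its wording is strong: "Subjects MUST discontinue study treatment and withdraw from the study for any of the following reasons". But it applies to four listed reasons. Its adverse-event ground is itself about whether continued participation serves the patient, and 8.2.1 handles other toxicity by reducing or interrupting drug. SALT is taken at early termination. The section 7.1 sentence "All patients will be seen at 8, 16, and 24 weeks after completion of study drug" can be read as covering completers, so it does not clearly contradict 7.7. What is missing is narrower: whether the early-termination value counts, and who is in the denominator.

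The 60 subjects in 13.2, against 15 elsewhere, is a clerical slip in accrual text and has no bearing on the endpoint.

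**Conclusion.** The concern holds in two parts. First, the primary endpoint has two time points in current text, and they can give different rates: 27% against 40% in the assumed example, with the comparison against 10% affected only near 4 of 15. Second, no efficacy set is defined, and no rule says how a patient who stops before week 24 counts. In the assumed example that moves the estimate by up to 10 points and changes no conclusion.

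The documents do not support the inference that the sample size calculation is wrong. The stated power reproduces for 15 evaluable patients. It falls below 80% only if early stoppers count as non-responders and more than about 15% stop early, and the documents give no rate by which to judge whether that is likely.

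This should be corrected. It is a fault of definition that is cheap to repair, and it does not undermine the design.

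**What to change.** 1. **Primary visit.** Word it identically in the synopsis, 5.1, 11.1 and 13.3. The smallest edit is to bring 11.1 into line with end of treatment. Then report response at week 24 in all patients as a named secondary result, since it is the one on-treatment time point they share before the response-dependent extension. If week 24 is chosen as primary instead, report end of treatment as the secondary.

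2. **Efficacy set and counting rule, in 13.2.** State that:
   - the primary efficacy set is all patients who receive at least one dose;
   - a patient who permanently stops study drug before the week 24 visit, or has no SALT at the primary visit, counts as a non-responder;
   - a patient who stops during the extension is classified by the last on-treatment SALT if the primary visit is end of treatment, or by the week 24 SALT if it is week 24;
   - use of early-termination SALT, and a completers analysis, are sensitivity analyses.

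   Correct 60 to 15 in the same section.

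3. **Reconciliation.** Sections 7.1, 7.7, 9.2, 9.2.1 and 12.9.2 should be made consistent on whether stopping drug also ends study visits. No rule is proposed here.

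**Cost.** Items 1 and 2 are text edits and need no new assessments, because SALT is already scheduled at every visit. The reported rate may be lower than a completers rate (10 points lower in the example of 3 early stoppers), and power against 10% falls with early stopping as tabulated.

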#### Secondary Endpoints

1. Percent hair regrowth from baseline determined by SALT measurements following end of treatment (week 24 to 72) and during the observational phase at 8, 16, and 24 weeks after end of treatment.
2. Comparison of the proportion of responders in the experimental group with the historically known placebo response rate (<10%), with response defined as 50% change in SALT score (50% regrowth) from baseline, at end of treatment (week 24 to 72), and during the observational phase at 8, 16, and 24 weeks after end of treatment.
3. Comparison of the proportion of subjects in each group attaining global overall improvement SALT score of A5 (100% coverage) supported by  $\leq$  SALT 25% at the end of treatment (week 24 to 72), and during the observational phase at 8, 16, and 24 weeks after end of treatment.
4. Change in PGA (Physician Global Assessment) based on live evaluations and evaluation of standardized photographs between baseline, and selected subsequent visits during the treatment period and the follow up period.
5. Change in patient global assessment between baseline, and subsequent selected visits during the treatment period and the follow up period.
6. Change in patient quality of life assessment from baseline to and each subsequent visit during the treatment period and the follow up period.
7. Frequency of occurrence and timing of relapse (as defined above) in responders followed for 6 months off therapy.
8. Safety will be evaluated as a secondary endpoint using descriptive statistics to summarize the cumulative incidence and types of AEs.
9. The proportion of patients who discontinued treatment will be summarized.

10.

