
Criteria for Evaluation: (Efficacy, safety, stopping rules, etc.)
	
EFFICACY
 
Primary endpoint: SALT (Severity of Alopecia Tool) Scores: The proportion of scalp involvement is determined by dividing the scalp into 4 quadrants and estimating the percentage of the scalp surface that all the alopecic areas would occupy if placed together.
 
Secondary endpoint: Changes in hair re-growth as a continuous variable will be determined using physical exams and Canfield photography, as well as patient and physician global evaluation scores. Additionally, patient reported outcomes, safety measures, incidence and timing of relapse will be important secondary outcomes.
 
To assess safety, frequent and close monitoring of clinical and laboratory findings have been implemented. Adverse events will be captured and analyzed as a secondary endpoint.
 
All physical examination findings, vital sign abnormalities, and clinical laboratory abnormalities, will be captured as AEs when deemed medically significant by the investigator. A qualified physician associated with the study will be available to assess clinical signs and symptoms that may be indicative of an adverse event. Safety will be assessed by summarizing the incidence and type of AEs. The proportion of patients who discontinued treatment will be summarized.

---	---

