### 2.3.4 Overall safety of Tofacitinib

Safety analyses of pooled data of tofacitinib-treated patients show a similar serious infection rate to biologics of 2.7/100 patient-years with opportunistic infections including tuberculosis, fungal infections, and pneumocystis reported. Screening for latent tuberculosis is recommended. The frequency of serious infections was increased in patients over the age of 65. In long-term extensions, a slightly higher rate of infections and nonmelanoma skin cancers was seen in the 10-mg p.o. b.i.d. studies, and this dose was therefore not approved by the FDA. However, a higher incidence ratio (4.5) of herpes zoster was seen compared to other biologics (1.32). There was no association with neutropenia, lymphopenia, or concomitant

nonbiologic DMARDs. No safety data are available on impact of tofacitinib on patients with chronic viral hepatitis reactivation, as these patients were excluded from the trials. Prophylactic vaccination for herpes zoster and hepatitis B should be updated prior to treatment whenever possible, and live virus vaccination during treatment should be avoided.

Malignancies including lymphoma have been reported in conjunction with treatment with tofacitinib, and Epstein-Barr virus lymphoproliferative disorders were seen in renal transplant studies.

GI perforations occurred in 10 of 5,043 tofacitinib-treated patients in analysis of pooled study data from ORAL trials with long-term extensions resulting in 0.144 events per 100 patient-years. Six of these cases were diverticular in nature, three were appendiceal perforations, and one an isolated gastric ulcer.

Laboratory-test monitoring should include initially a complete blood count (CBC), comprehensive metabolic panel (CMP), and fasting lipid panel. Minor decreases in absolute lymphocyte, neutrophil, and red blood cell counts were seen in less than 1% of patients.

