#### Week 28 to 72 (Optional treatment extension)

The treatment duration may be extended by up to 12 additional months beyond the initially scheduled 6 months of treatment, if clinically indicated and at the discretion of the investigator. Patients will continue to be seen monthly while on extended tofacitinib treatment. Assessments of disease severity will continue to be performed via physical exam and photography, and will be objectively quantified using the SALT and Physician global assessment (PGA). Patient global assessment and patient quality of life assessment will also be completed.

PGA and patient evaluations will be based on similar 100mm visual analog scales with 0 labeled as no scalp hair loss and 100 labeled as complete scalp hair loss. Patients and physicians will place a vertical mark along the horizontal line depending on their assessment of the degree of hair loss present at the time of assessment.

Patient quality of life assessments will be based on changes in the Dermatology Life Quality Index DLQI, which we have previously used for patient evaluation in the AA registry, and the Skindex-29 Questionnaire.

Photography will be performed at all visits.

Optional additional biopsies and blood draws may be obtained at the investigator's discretion and with the subject's permission as indicated by clinical considerations such as variation in the timeline to regrowth from one subject to another, focal apparent resistance to treatment, as well as other potential unpredictable clinical occurrences. Unscheduled biopsies and blood draws will ensure that tissue and blood samples can be obtained at optimal time points to evaluate the changes occurring in response (or lack of response) to treatment. The patient will be given the option to agree to, or decline, the additional biopsies and blood draws.

Adverse events will be assessed at every visit.

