### **13.4.2 Safety Analyses**

To assess safety, we will summarize the incidence of adverse events for the study group. Analysis of safety is included as a secondary endpoint. All subjects will receive tofacitinib and will be evaluated for safety. Safety outcomes include adverse events, clinically significant changes in vital signs, laboratory test abnormalities, and clinical tolerability of the drug. The investigator will determine the severity of each adverse event as mild, moderate, severe, or very severe. Laboratory findings that the investigator feels are clinically relevant should be recorded as adverse events. In addition, the investigator will determine the relationship of the adverse event to the administration of the study drug. Any occurrence of a SAE from time of consent forward, up to and including follow-up visits will be reported. See Section 12 for the SAE reporting procedures.

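### Adverse events are summarised as crude incidence with no time point or exposure denominator, although time on drug can run from 24 to 72 weeks at investigator discretion

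*Combined protocol and SAP*

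**What the plan says.** Every statement on the analysis of adverse events describes an incidence in a single group. The synopsis says "Safety will be assessed by summarizing the incidence and type of AEs". Secondary endpoint 8 in Section 13.3, repeated in Sections 5.2 and 11.1.1, says safety will be evaluated "using descriptive statistics to summarize the cumulative incidence and types of AEs". Section 13.4.2 says "we will summarize the incidence of adverse events for the study group". None of these gives a time point, a person-time denominator, a rule for subjects observed for less time, or a split between on-drug and off-drug periods.

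Exposure is not fixed. The synopsis says the drug "will be taken orally twice a day for up to 24 to 72 weeks". Section 7.1 says "The treatment duration may be extended by up to 12 additional months beyond the initially scheduled 6 months of treatment". The synopsis makes this conditional: treatment "may be extended by up to 12 additional months if clinically indicated with an acceptable lab safety profile, at the discretion of the investigator". Dose varies too: it "may be increased up to 10mg PO BID, if clinically indicated at the discretion of the investigator".

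Observation also continues off drug. Section 7.1 has adverse events assessed at visits 8, 16 and 24 weeks after treatment ends. Section 11.1.1, however, does not require nonresponders to take part in that follow-up.

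**The concern.** A percentage of subjects with an event can be interpreted only if the period it covers is known. Here that period differs between subjects, and a clinical decision sets it rather than the design. Two studies with the same underlying risk would report different percentages if one investigator extended more subjects than the other.

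The exposure is also informative. Because extension needs an acceptable laboratory profile, subjects with laboratory abnormalities may contribute less time on drug than the others.

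Safety is a named secondary endpoint, and Section 4 says a positive result would be the basis for designing larger trials. A designer of such a trial would want the risk over a stated period, and the planned summary does not give it.

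**Working it through.** The plan states no safety figure to reproduce. Its one design calculation, the power statement in Section 13.1, concerns response rates and does not enter here.

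**Inputs from the documents.** There are 15 subjects (Section 13.1), 24 to 72 weeks on drug (synopsis), 24 weeks of off-drug follow-up (Section 7.1), and a background serious-infection rate of 2.7 per 100 patient-years (Section 2.3.4). **Assumptions of this check:** a year of 52.18 weeks, a constant hazard, and illustrative event rates of 0.1 to 2.0 per patient-year. The documents give no overall adverse-event rate.

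**1. On-drug person-time, as bounds.**
- All stop at week 24: 15 × 24 / 52.18 = 6.9 patient-years.
- All reach week 72: 15 × 72 / 52.18 = 20.7 patient-years.
- Ratio: 72 / 24 = 3.0.

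**2. Crude incidence at an unchanged risk.** Incidence = 1 − exp(−rate × weeks / 52.18).

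| Rate per patient-year | By week 24 | By week 72 | Ratio |
|---|---|---|---|
| 0.027 (Section 2.3.4) | 1.2% | 3.7% | 2.96 |
| 0.1 (assumed) | 4.5% | 12.9% | 2.87 |
| 0.5 (assumed) | 21% | 50% | 2.43 |
| 1.0 (assumed) | 37% | 75% | 2.03 |
| 2.0 (assumed) | 60% | 94% | 1.56 |

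At 0.027, the chance of at least one case among 15 subjects is 1 − exp(−0.027 × 6.9) = 17% at one bound and 1 − exp(−0.027 × 20.7) = 43% at the other.

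**3. Dependence on how many are extended.** At 0.5 per patient-year, with a share s of subjects treated to week 72 and the rest to week 24, expected incidence is (1 − s) × 20.5% + s × 49.8%. This is 20.5% for s = 0, 35.2% for s = 0.5 and 49.8% for s = 1. The risk is the same throughout; only the extension decision changes.

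**4. The reverse reading.** Suppose 3 of 15 subjects (20%) have an event, with full exposure counted for each. That is 3 / 6.9 = 43 per 100 patient-years if everyone had 24 weeks, and 3 / 20.7 = 14 if everyone had 72.

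**5. Total observation, on and off drug.** If everyone completes follow-up, it runs from 24 + 24 = 48 weeks to 72 + 24 = 96 weeks, a ratio of 2.0. If a nonresponder stops at week 24 and skips follow-up, the range is 24 to 96 weeks, a ratio of 4.0.

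**6. What a rate could show with 15 subjects.** With no events, the exact two-sided 95% Poisson upper limit is 3.69 events. That is 3.69 / 6.9 = 53 or 3.69 / 20.7 = 18 per 100 patient-years. One event in 20.7 patient-years gives 4.8 per 100 (95% CI 0.1 to 27).

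**The case against.** The case for leaving the plan alone has several parts.

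- **The study is small, uncontrolled and descriptive.** No treatment contrast is biased and no decision rule changes. This is true, and it limits the weight of the point.
- **Incidence is not all that is recorded.** Sections 12.4 and 13.4.2 also cover onset, duration, severity, relatedness, laboratory and vital-sign changes, and discontinuations are summarised. A reader might infer that on-drug and off-drug events could never be separated. The documents do not support that: with onset recorded, the data allow it. What is missing is the tabulation.
- **Cumulative incidence could mean a time-indexed estimate that allows for censoring.** That would meet much of the point, but no time point or estimator is given, and Section 13.4.2 says only incidence.
- **The hazard may not be constant.** Section 2.3.4 says creatinine changes generally peaked at six weeks and lipid changes were generally present by then. For such events, incidence would rise little after week 24, and a rate per patient-year would dilute the risk in extended subjects. This stands. It is a reason not to rely on a rate alone.

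A reader might also infer that the plan fails because it cannot be compared with the background rate ("similar serious infection rate to biologics of 2.7/100 patient-years"). No planned analysis makes that comparison, and step 6 shows that a rate from 15 subjects could not make it firmly. Nor do the documents support comparing rates by dose. Everyone starts at the lower dose and increases are discretionary, so dose is confounded with time on study and clinical course.

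**Conclusion.** The point holds as a modest and inexpensive improvement to the analysis. As written, the safety percentage depends on how many subjects were extended and followed as well as on risk. At the bounds of planned exposure (6.9 and 20.7 patient-years), an unchanged risk gives a percentage about 3-fold higher for rare events and about 1.6- to 2.4-fold higher at 0.5 to 2.0 events per patient-year.

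These sizes rest on a constant hazard and on all subjects sitting at one extreme or the other. With a mix of durations, expected incidence falls between the bounds, early discontinuation would lower exposure, and early-onset events would differ less.

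A reader might conclude that dividing events by patient-years settles the matter. It does not, because extension depends partly on laboratory safety and time on drug is therefore related to the outcome. A fixed early window, over which treatment is planned for everyone and before any extension begins, is the sounder main summary.

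**What to change.** Amend Section 13.4.2, and align item 8 of Section 13.3 with it, as follows.

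1. Make adverse-event incidence through week 24, in all treated subjects, the main safety summary. State how subjects who leave earlier are handled.
2. Report total on-drug and off-drug person-time, and tabulate events by whether onset was on or off drug.
3. Add events per 100 patient-years with exact Poisson 95% intervals, labelled as a descriptive supplement.
4. List the dose being taken at onset for each event, without comparing rates by dose.

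The off-drug denominator needs a single collection window. Section 12.5 collects serious events for 30 days after the last dose, with later events only if related to the drug or a protocol procedure. Section 13.4.2 reports them through the follow-up visits. These passages must be reconciled.

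No new assessment is needed: event onset is captured under Section 12.4, and dosing dates come from the diaries and drug reconciliation in Section 8.5. The cost is a few table columns. The intervals will be very wide with 15 subjects and will not support a firm comparison with the rates in Section 2.3.4.
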